Social VR intervention is developed to enhance the social interaction skills of children. The participants will wear a head-mounted display (HMD) for the Social VR intervention. Each session of the Social VR intervention lasts for a maximum of 20 minutes to ensure the participants focus on the intervention and prevent causing any physical effect. The duration will be adjusted depending on the emotion of the participants during the intervention. The Social VR intervention will mainly help the participant to enhance their social interaction skills and executive function. The intervention contains three real-life virtual scenarios, including (1) classroom and playground, (2) MTR station and compartment, and (3) street and building. One scenario will be adopted in each session. The sequences of the scenarios used in each session will be the same for all participants. During the Social VR intervention, one RA will also appear as one avatar in the scenario to guide the participants to complete a series of tasks. Each intervention session will be conducted in a classroom independently for each participant.

Traditional social skills training

An experienced SEN teacher will teach the participants social interaction skills through tradidactic instructions and role-play activities. Four modules will be covered in the 3-week training: (1) how to introduce yourself and basic social skills; (2) how to listen to others; (3) how to share with others; (4) learn to know how people feel and how to empathise. These modules have been applied in many studies. The content of this training will be as similar as possible to the Social VR training. The training lasts 20 minutes which depends on the emotion of the participants. Each training session will be conducted in a classroom independently for each participant.

Waitlist control group

The participants in this group will receive no training and they can participate in the social VR training after the intervention period. To ensure consistency of the experiment, the participants are not allowed to initiate or change their pharmacological treatment during the 3-week intervention period.

Measures

Questionnaires

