The parents or legal guardians of the participants will complete a structured questionnaire at the baseline and after the last session. Demographic information, including age, gender, Medication, ADHD symptoms and game experience will be recorded at the baseline. The questionnaires include questions about social skills and executive functioning. The satisfaction of the participants and their parents or legal guardians towards the training program will be assessed at week 3. The VR sickness of the participant will be evaluated after each session. The assessor will be blind to the treatment condition. The questionnaires will include the following scales:

Primary outcome measure

1. Process evaluation

The process evaluation of the training will be assessed by investigating: (i) training acceptability as measured by the participants' attendance and compliance; (ii) recruitment rate; (iii) participant completion.

(i) Assessment of training acceptability and compliance

The attendance of the participants during the trainings will be recorded. To verify the validity of the findings, training non-adherence of the participants will be terminated which will be stated in the consent form. The absence of any training session will be considered as non-adherence. The participants will be asked about their willingness of partaking in this kind of training by one 7-point Likert scale question which is used to reflect the acceptability to the intervention. The retention rate should be at least 85% according to the feasibility RCT.

The compliance with the training program will be evaluated by the communication log which the parents record their children's daily activity and emotion in the 3-week intervention period. The participants' parents will be reminded to attend the training through telephone in the first four training sessions and WhatsApp or WeChat in the fifth and eighth training sessions. No reminder follow-up will be made in the remaining four sessions. These data will be used to evaluate their compliance.

(ii) Recruitment rate

The recruitment rate is at least 48.5% of all referrals according to the feasibility study.

(iii) Participant completion

Participants attending at least nine (i.e., 75%) of the 12 sessions are considered to have completed the program.

Secondary outcome measure

1. Social Skills Rating Scale (SSRS-P)

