The social skills of the children will be assessed by Chinese-translated SSRS-P which will be scored by the participants' parents before the first session and after the last session. This scale consists of 3 subscales, including self-control, assertiveness and initiative and cooperation, with a total of 31 items. A 3-point Likert scale (never, sometimes, often) is used to score. The SSRS-P is a validated instrument that has been commonly adopted in clinical trials of psychiatric and neurological disorders.

2. Child psychologist's assessment

One child psychiatrist will score the performance of the participants in the 5-minute tasks to obtain an objective evaluation. Broken blinding is unavoidable in child psychiatrist's assessment. To minimise unblinding bias during the assessment, each participant will be identified by a case number.

3. Behaviour Rating Inventory of Executive Function (BRIEF)

Chinese-translated BRIEF used to assess the executive functioning of children which will be scored by the participants' parents before the first session and after the last session. The subscales of inhibitions (16-item) and emotional control (10-item) will be adopted in this study. A 3-point Likert scale (never, sometimes, often) is used to score.

4. Satisfaction

Satisfaction is measured by a 7-point Likert scale, 'What grade would you give to this training program?'. Both participants and parents/ guardians have to answer.

5. Simulator Sickness Questionnaire (SSQ)

The SSQ measures motion sickness or physical discomfort of participants in VR environment. Nine items will be measured, including discomfort, fatigue, headache, eyestrain, sweating, nausea, difficulty concentrating, blurred vision and dizziness, with yes or no questions for each item.

6. Assessment of safety

a) Adverse events

RA1 will ask participants' parents/ guardians, using open-ended questions, whether the participants experienced any adverse events during training. The severity and relationship of the adverse event to the intervention will be documented and investigated.

b) Reasons for withdrawal

When a subject withdraws before completing the study, the reasons for withdrawal will be recorded.

Statistical analysis plan

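### VR symptoms are recorded only as yes/no, and no rule carries a positive answer into the parent-based adverse-event process where severity and relationship are documented

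*Combined protocol and SAP*

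**What the plan says.** Safety information comes through two separate streams, both listed under Secondary outcome measure.

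The first is the SSQ (item 5). Its stated scope is VR: "The SSQ measures motion sickness or physical discomfort of participants in VR environment". It has nine symptoms, the list ending "blurred vision and dizziness, with yes or no questions for each item". The Questionnaires section gives the timing: "The VR sickness of the participant will be evaluated after each session". The respondent is not named.

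The second is adverse events (item 6a): "RA1 will ask participants' parents/ guardians, using open-ended questions, whether the participants experienced any adverse events during training". Then: "The severity and relationship of the adverse event to the intervention will be documented and investigated". The timing and frequency of the parent question, the severity scale and the person who judges relationship are not given.

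On who is present, the Social VR Intervention section says "Each intervention session will be conducted in a classroom independently for each participant" and that "one RA will also appear as one avatar in the scenario to guide the participants". The Traditional social skills training section has an SEN teacher working with each child separately. Neither section mentions a parent. The text on acceptability and compliance, however, says: "The participants' parents will be reminded to attend the training through telephone in the first four training sessions".

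Reasons for withdrawal are recorded (item 6b). The Statistical analysis plan contains no analysis written specifically for the SSQ or for adverse events.

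**The concern.** The instrument used closest in time to VR exposure cannot grade what it finds, and the process that can grade has no stated input from that instrument. Nor does it have a stated input from the child or from the staff who run the sessions. It depends on what a parent knows and chooses to mention in answer to an open question.

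This matters in this trial for three reasons. First, the plan foresees physical reactions, since avoiding them is one reason given for the 20-minute limit on a VR session. Second, acceptability and compliance form part of the primary outcome, and whether symptoms are trivial or marked bears on how those results are read. Third, waitlist children may take the VR training afterwards, so up to 30 more children depend on what is learned about tolerability.

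At the end of the trial the adverse-event table could show few VR reactions beside an SSQ table that shows many, with no means of saying whether any of the latter was more than mild.

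**Working it through.** The plan states no figure on this point to reproduce. The check sets the passages side by side and follows an event through them.

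- **Symptom positive on the SSQ, and a parent mentions it to RA1.** It becomes an adverse event under item 6a, and its severity and relationship are documented and investigated.
- **Symptom positive on the SSQ, and no parent mentions it.** A yes is stored for that item and session. No text asks for severity or relationship, or sends it to the adverse-event process.
- **Event noticed only by the session RA or SEN teacher.** No text makes either of them an adverse-event source. The event is recorded only if a parent raises it, or as a withdrawal reason if the child leaves the study.
- **Event in the traditional arm.** The SSQ concerns VR and does not apply. The parent question is not limited to VR, so the event can reach the record that way.

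The gap therefore lies in the second and third cases.

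Scale, from the plan's own inputs:

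- Children in the social VR group: 30 (Sample size).
- Sessions per child: 12 (Methods/ Design).
- SSQ items: 9 (Secondary outcome measure, item 5).
- SSQ administrations: 30 × 12 = 360.
- Item answers: 360 × 9 = 3,240.

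Both totals are upper limits for the randomised VR arm, since they assume full recruitment and attendance. The 360 is the more useful figure, because the 3,240 includes every no, which needs no severity.

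The documents give no expected symptom rate. As an assumption only, if 5% to 20% of VR sessions produced at least one yes, the number of symptomatic sessions would be 0.05 × 360 = 18 to 0.20 × 360 = 72. How many of these would also reach the adverse-event record through a parent cannot be derived from the documents.

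**The case against.** A pilot with process measures as its primary outcome may reasonably keep a tolerability checklist apart from adverse-event reporting. The SSQ also retains more than a single tally: which symptom, how many, and how often over 12 sessions. Severe nausea and slight eyestrain are different items and would not give the same record. Only severity within an item is lost. All of this stands, and it limits the point without removing it.

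Four stronger readings are tempting, and the documents do not support them:

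- *VR reactions are never graded or investigated.* A reaction that a parent reports would be, under item 6a.
- *Traditional-arm events have no route to the record.* The parent question covers all participants, and withdrawal reasons are recorded as well.
- *Parents are absent, and the child answers the SSQ.* Individual sessions do not exclude a parent. The reminder wording may mean that parents sit in, or only that they bring the child. The SSQ respondent is simply not stated.
- *A definite number of events will be missed.* Assuming that parents report half of 18 to 72 symptomatic sessions gives 9 to 36 missed, but that only restates two assumptions.

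Other sources close little of the gap. Withdrawal reasons do not cover a child who cuts one session short and returns. The parents' communication log records daily activity and emotion, and is kept to assess compliance.

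A fair warning about remedies also stands. Entering every SSQ yes as an adverse event would raise counts in the VR arm alone, because only that arm has a prompted checklist. Moreover, difficulty concentrating overlaps with ADHD itself, and no pre-session SSQ is described.

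**Conclusion.** The point holds as a gap between two collection methods. SSQ symptoms are held as yes/no, no rule links a positive item to the adverse-event process, and that process is described only through open-ended questions to parents, whose presence in sessions is unclear. Reactions found only on the SSQ, or events seen only by session staff, may go ungraded and uninvestigated unless a parent reports them.

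The gap touches up to 360 SSQ administrations. The number of symptoms affected is unknown, and the 18 to 72 symptomatic sessions rest wholly on the assumed 5% to 20%. The conclusion itself rests on what the text states and leaves unstated. It would weaken if an operational document already linked the SSQ to adverse-event review or gave session staff a reporting duty, but nothing in the protocol or analysis plan does so.

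**What to change.** In Secondary outcome measure, items 5 and 6(a):

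1. Keep the nine SSQ items and state who answers them.
2. For each yes, record severity and relationship to the intervention, using the same categories as for adverse events, and state what those categories are. Report these in the SSQ table, separately from the adverse-event counts.
3. In both training arms, at the end of each session, ask the child and the session RA or SEN teacher the same open-ended adverse-event question, alongside the parent question. In the VR arm, ask it before the SSQ, so that the checklist does not prompt answers in one arm only.
4. Say whether parents sit in on sessions.
5. State that the waitlist adverse-event count will not be compared directly with the training arms, because that arm has no sessions and so no added source.

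The cost is slightly more form-filling and a higher count of mild events. Ascertainment by the open question is then the same in the two training arms, and the prompted VR symptoms can be read on their own.

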The study targets children with diagnosed ADHD and aims to (1) develop a social virtual reality-based intervention, (2) investigate its effects on improving the social skills and executive functioning of inhibitions, emotional control and attention of the children compared to traditional social skills training and (3) evaluate the subjects acceptability and compliance with social VR training for enhancing social interaction skills. It is hypothesised that the social interaction skills of the participants in the social VR training group are likely to perform better than those in the traditional social skills training group. Participants in the waitlist control group will receive no change in social interaction skills compared with the two intervention groups.

Methods/ Design

The study will be a three-arm randomised controlled trial comparing the effects of a social VR-based intervention with traditional social skills training on social skills and executive functioning of children with ADHD. Participants in the social VR intervention group and traditional social skill training group will receive 12 training sessions for 3 weeks (4 sessions per week), and participants in the waitlist control group will be asked to retain their usual lifestyles for 3 weeks. The overall design of the study is illustrated in Figure 1. Ethical

approval for the study has been obtained by the Human Subjects Ethics Application Review Committee of The Hong Kong Polytechnic University.

[figure not shown]

Figure 1. Study design

Participants

Individuals who meet the inclusion criteria will be recruited. The criteria are as follows: 1) aged between 6 and 12 years; 2) ethnic Chinese; 3) residing in Hong Kong; 4) having received a diagnosis of ADHD by Child Assessment Service in Hong Kong or via private practice; 5) stable on pharmacological and/or psychological treatment for ADHD 8 weeks before baseline (determined by health care professionals on the basis of medication data and behavioural observation); 6) no initiation or change of pharmacological treatment for ADHD during the intervention period; 7) ability to read Chinese, and speak and listen to Cantonese by the child and by at least one of their parents or legal guardian; 8) willing to provide informed consent by both participants and one of their parents or legal guardian.

Exclusion criteria are as follows: 1) comorbid autism; 2) mental retardation; 3) an estimated

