All statistical analyses will be performed in SPSS version 26.0 software (IBM Corp, Armonk, NY, USA) and are two-sided with a level of significance of < 0.05 . Demographic information of the participants will be summarised with frequency and percentage for categorical variables. The continuous variables will be summarised by mean and standard deviation. The change between baseline and week 3 within each arm will be tested using t-tests. To examine the between-group difference in terms of measure outcomes from baseline to week 3, repeated analyses of covariance (ANCOVA) with adjustment of baseline characteristics will be conducted. To evaluate the improvement during the intervention period among the three groups, f-tests will be performed on primary and secondary outcome measures at the beginning of the first session and at the end of the last session. An intention-to-treat analysis will be performed. This analysis is regarded as the most appropriate approach to analyse RCT data by the highest-quality journals, which have utilised the CONSORT standard.

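### The adverse-event question is tied to training, so the plan specifies no comparable adverse-event data for the waitlist arm

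*Combined protocol and SAP*

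**What the plan says.** Safety is the sixth secondary outcome. The only rule for collecting adverse events is in item 6(a): a research assistant asks parents or guardians, in open-ended form, "whether the participants experienced any adverse events during training". For each event, "The severity and relationship of the adverse event to the intervention will be documented and investigated".

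The Waitlist control group section states: "The participants in this group will receive no training and they can participate in the social VR training after the intervention period". Methods/ Design adds that "participants in the waitlist control group will be asked to retain their usual lifestyles for 3 weeks". The two trained arms each have 12 sessions over the same 3 weeks.

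The Statistical analysis plan names no summary or test for adverse events. The nearest statement is general: to evaluate improvement among the three groups, "f-tests will be performed on primary and secondary outcome measures", taken at the start of the first session and the end of the last.

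**The concern.** The event window is defined by an exposure that one arm does not have. A research assistant who follows the text literally has nothing to ask a waitlist family during the 3 weeks. If the waitlist children later take up social VR, the literal question would apply to them only then, when they are no longer untreated.

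Headache, tiredness or a poor night's sleep can occur in any child over three weeks. The plan asks for a judgement on whether each event is related to the intervention. A concurrent untreated rate is the natural reference for that judgement, and the trial has already randomised 30 children who could supply it.

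The wording is also unclear for the trained arms. If it refers to the sessions themselves, a symptom that appears the same evening falls outside the question, although a parent is well placed to notice it.

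**Working it through.** The plan states no adverse-event rate, expected count or safety precision, so there is no figure to reproduce. The check is what each reading of the wording would deliver.

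**Inputs**
- Sessions per trained arm: 12 over 3 weeks (Methods/ Design).
- Session length: at most 20 minutes for social VR, 20 minutes for traditional training (the two intervention sections).
- Children per arm: 30 (Sample size).
- Waitlist training in the 3 weeks: none (Waitlist control group).
- Probability *p* that a child has some background event in 3 weeks: not in the documents. Assumed 5% to 30%, for illustration only.

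**Reading A: in-session only**
- Window: 12 × 20 = 240 min = 4 h. Three weeks: 21 × 24 = 504 h. Share covered: 4/504 = 0.8%.
- If background events fall evenly over time, the chance that a child has one in-session is q = 1 − (1 − p)^(240/30,240), where 30,240 is the number of minutes in 3 weeks.
- Expected number of children per arm, 30q: 0.012 at p = 5%, 0.025 at 10%, 0.053 at 20%, 0.085 at 30%.
- Almost no background events enter the trained arms' counts. The loss is everything between sessions, and the waitlist has no window.

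**Reading B: the 3-week programme, trained arms only**
- Expected children with a background event per trained arm, 30p: 1.5, 3, 6 and 9 at p = 5%, 10%, 20% and 30%.
- Between-session events are captured. The waitlist is not asked, so the trained arms' counts have no untreated counterpart.

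**Reading C: the 3-week period, all arms**
- The same 30p is expected in every arm. There is no defect.

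**Which contrasts survive**
- Social VR against traditional training: same question and same schedule under A, B and C, so randomisation balances background events in expectation.
- Either training against no training: interpretable only under C.

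**Not asked is not the same as none**
- If all 30 waitlist families were asked and none reported an event, the two-sided 95% exact upper limit would be 1 − 0.025^(1/30) = 11.6%. That is imprecise, but it is information.
- If they are not asked, there is no numerator and no interval.

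**The case against.** The best defence is that the sentence refers to participants' parents without limiting it to trained arms, and that the protocol elsewhere describes the traditional programme as a 3-week training. The phrase could therefore mean the whole 3-week period for everyone, which is reading C. This is possible, but the text does not say it. The waitlist section describes that arm as having no training and uses a different term, the intervention period, for the shared calendar window. The ambiguity stands.

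Other data partly cover the gap. VR sickness is assessed after each session with nine yes/no items, and relatedness is considered event by event. The sickness items concern the VR environment, so they give nothing for the waitlist. The parents' daily log of activity and emotion is kept to assess compliance and is not an adverse-event record.

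Three stronger readings are tempting, and the documents do not support them.
- A reader might infer that the waitlist will show zero events and the trained arms a spurious significant excess. Waitlist events would be uncollected, not zero. The excess needs reading B, an assumed background rate, the blank treated as 0 of 30, and a trained-against-waitlist test that the plan does not name. The three-group F-tests concern improvement from first to last session, and no baseline adverse-event measurement is described.
- A reader might infer that effects of VR cannot be separated from background at all. The traditional arm answers the same question over the same schedule, so an excess specific to VR can be assessed.
- A reader might infer that parents cannot see the sessions they are asked about. The documents do not say whether parents attend.

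**Conclusion.** The point holds as a gap in specification. The plan provides no adverse-event question or window for the waitlist that matches the trained arms. Training against no training therefore cannot be read for safety, and the one untreated arm contributes no background rate. Harms common to both trainings would not show in the remaining VR-against-traditional contrast.

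On the in-session reading, the trained arms are also observed for only 0.8% of the 3 weeks. This figure assumes 12 sessions of the full 20 minutes. On a common 3-week reading the problem disappears, which is a reason to write that reading down.

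The number of events affected cannot be given, because it depends on a background rate that the documents do not state. This is a minor point for a pilot whose primary outcomes are process measures, but it is cheap to correct.

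**What to change.** 1. Reword item 6(a) so that the question covers any adverse event from baseline to week 3, whether or not it occurred in a session.
2. Put the same open-ended question to parents in all three arms at the same time, at least with the week-3 questionnaire. For the waitlist, which has no last session, state that this means the end of the 3 weeks.
3. Add to the Statistical analysis plan a table of the number and proportion of children with any event, by arm, with exact (Clopper-Pearson) 95% intervals, and exclude adverse events from the general F-test statement.
4. Report events during the waitlist's later VR access separately, so that they are not counted in the untreated period.

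The cost is one reworded question on an existing contact and one table. It needs no extra staff or visits; weekly calls and questioning each child after every session are not required. The downside is a few more unrelated events to document, and some recall error from asking once over three weeks, which should be similar across arms if the question is put identically.

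### Every efficacy score is tested at two-sided 0.05 with no lead score or contrast and no exploratory label, so the 5% level does not hold for the efficacy results as a set

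*Combined protocol and SAP*

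**What the plan says.** The Statistical analysis plan sets one rule for all analyses: they "are two-sided with a level of significance of < 0.05". It then lists three kinds of test.

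- Within arms: "The change between baseline and week 3 within each arm will be tested using t-tests".
- Between groups: "repeated analyses of covariance (ANCOVA) with adjustment of baseline characteristics will be conducted".
- In addition: "f-tests will be performed on primary and secondary outcome measures at the beginning of the first session and at the end of the last session".

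The efficacy scores appear under Secondary outcome measure.

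- SSRS-P: "This scale consists of 3 subscales, including self-control, assertiveness and initiative and cooperation, with a total of 31 items". The text does not say whether the subscales, a total or both are analysed.
- Psychiatrist's assessment: "One child psychiatrist will score the performance of the participants in the 5-minute tasks". The number of scores is not stated.
- BRIEF: "The subscales of inhibitions (16-item) and emotional control (10-item) will be adopted in this study".

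The primary outcome is not an efficacy score. Under Primary outcome measure, "The process evaluation of the training will be assessed by investigating" introduces acceptability, recruitment rate and completion.

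The rationale just before Aims and hypotheses nevertheless asks whether VR training is more effective than traditional training. The hypothesis in that section is that the VR group will do better on social interaction skills. No multiplicity rule, testing order, lead contrast or exploratory label appears in the protocol or SAP.

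**The concern.** A 0.05 threshold limits false positives to 5% for one test. When several scores are each tested at 0.05, and possibly by more than one method, the chance that at least one crosses the line by luck is higher. Nothing in the plan says which result answers the efficacy question. A report could therefore rest its effectiveness claim on whichever score or test reached significance and still follow the plan as written.

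This is a pilot whose results would shape a later trial. A chance finding could set that trial's choice of outcome or its expected effect.

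**Working it through.** **Inputs from the documents.** Three arms of 30 (Sample size; 3 × 30 = 90, as stated), two-sided 0.05, and the tests and scores listed above. The plan gives no familywise error rate to reproduce.

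**Assumptions.** One psychiatrist's score, pre-post correlation 0.6, between-score correlation 0.3 to 0.7, normal scores, complete data. The documents give none of these.

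**Step 1: number of p-values.**

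- Scores: 1 SSRS-P total + 1 psychiatrist + 2 BRIEF = 4, or 3 SSRS-P subscales + 1 + 2 = 6.
- Tests per score: 3 within-arm t-tests + 1 ANCOVA = 4 if the F-test is simply the ANCOVA's own. Separate F-tests at the first and last session add 2, giving 6.
- Low reading: 4 × 4 = 16. High reading: 6 × 6 = 36. Analysing SSRS-P subscales and total together gives 7 scores and up to 7 × 6 = 42.

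**Step 2: which tests bear on a group difference.** The within-arm t-tests do not compare groups. An F-test at the first session compares randomised groups before training. Neither enters the error rates below, which count only the ANCOVA and, where stated, the end-of-training F-test.

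**Step 3: independence as a reference.** With one test per score, the chance of at least one false positive is 1 − 0.95^k.

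- k = 4: 1 − 0.8145 = 18.5%
- k = 6: 1 − 0.7351 = 26.5%

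For a false result in one direction on one contrast, it is 1 − 0.975^k.

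- k = 4: 9.6%
- k = 6: 14.1%

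Positive correlation between scores lowers these figures. Using a second test per score raises them.

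**Step 4: simulation under no effect**, on the assumptions above:

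| Event | 4 scores | 6 scores |
|---|---|---|
| Any significant ANCOVA (three-group) | 14–17% | 18–24% |
| Any significant ANCOVA or end-of-training F-test | 20–26% | 25–36% |
| VR significantly better than traditional (ANCOVA contrast) on at least one score | 7–8% | 9–12% |

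Simulation error moves the ends of these ranges by about one percentage point.

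Pairwise contrasts are not specified, but the hypothesis needs one. If all three were run unadjusted on every score, the chance of any false contrast would be 28–41% for four scores and 35–55% for six. Those two ranges use between-score correlation 0 to 0.7 and pre-post correlation 0.5 and 0.7.

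**Step 5: what a single lead score achieves.** Naming one score is not enough. One score tested by both ANCOVA and the F-test has about an 8% chance of a false group difference. One score with three unadjusted pairwise contrasts has about 12%. One score, one test and one contrast gives 5%, or 2.5% in VR's favour.

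**The case against.** The best defence is that this is a pilot with a feasibility primary outcome. Every efficacy scale is secondary, the sample size follows pilot guidance, and strict error control over secondary outcomes in such a study is partly a matter of preference. That limits the harm. It would be a full answer if the plan called the efficacy tests exploratory. Instead the plan gives them all a significance threshold, and the protocol poses an efficacy question and hypothesis.

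It can also be said that the hypothesis concerns social interaction skills and that SSRS-P is listed first as the measure of social skills, so a lead is implied. This is partly right: the BRIEF subscales measure executive functioning and do not test that hypothesis. It still leaves open whether the SSRS-P total or its subscales decide, what role the psychiatrist's score has, and which test and contrast count.

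Three stronger readings are tempting, and the documents do not support them.

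- A reader might infer a minimum of 24 p-values. The text also allows 16, and most of the p-values in any count are within-arm or first-session tests that do not feed the error rate for a group difference.
- A reader might infer that a false group difference has at least a one-in-four chance. That holds for six scores when the ANCOVA and a separate F-test both count. On ANCOVA alone, with correlated scores, it is about 14–24%.
- A reader might take those figures as the chance of wrongly declaring VR better. They count differences between any arms in either direction. The figure for VR over traditional training is about 7–12%.

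**Conclusion.** The point holds and should be corrected. All efficacy tests are at two-sided 0.05, and nothing marks one as decisive or the rest as exploratory. With no true effect, the chance of at least one false group difference is about 14–24% from ANCOVA alone and about 20–36% with the end-of-training F-test added. For a false result favouring VR over traditional training, about 7–12% compares with the 2.5% that one two-sided test would allow in that direction.

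The ranges cover four to six scores and rest on the assumed correlations and on full arms of 30. The documents do not settle how many scores are analysed or whether the F-tests are separate from the ANCOVA, so no single figure can be given. What is missing is a lead efficacy test. The plan does have a primary outcome, and that outcome is not in question here.

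**What to change.** In the Statistical analysis plan, before any outcome data are analysed:

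1. Name one efficacy test at two-sided 0.05: the baseline-adjusted ANCOVA contrast of social VR versus traditional training on the SSRS-P total (31 items) at week 3.
2. Report everything else as estimates with 95% confidence intervals, labelled exploratory and without statements of significance. This covers the SSRS-P subscales, the psychiatrist's score, both BRIEF subscales, contrasts with the waitlist group, within-arm changes and any F-tests.
3. State that process evaluation remains the primary outcome.

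The score, the test and the contrast all have to be named, for the reason shown in step 5 of the working. The cost is a change of SAP wording and fewer results that can be called significant. No extra data or participants are needed.
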